## 10.2 Comparator vaccine

The comparator vaccines (HAVRIX® and TYPHIM Vi® and Menactra®) will be distributed to the study in single-use or multi-use vials per the manufacturer's recommendation and will be administered by IM injection on the schedules outlined in the Study Design (**Section 7**).

MenAfriVac comparator (Menactra® was previously used but another meningitis vaccine, the MenAfriVac® will be used) vaccine will also be offered to participants randomized to the Pfs230 arms at the end of the study.

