### **Not Related**

- does not have a temporal relationship
- OR
- definitely due to an alternative etiology

**Note:** Other factors (e.g., dechallenge, rechallenge) should also be considered for each causality category when appropriate. Causality assessment is based on available information at the time of the assessment of the AE. The investigator may revise the causality assessment as additional information becomes available.

The degree of certainty with which an AE can be attributed to administration of the study vaccine will be determined by how well the event can be understood in terms of one or more of the following:

- The event being temporally related with vaccination or reproduced on re-vaccination.
- A reaction of similar nature having previously been observed with this type of vaccine and/or formulation.
- The event having been reported in the literature for similar types of vaccines.
- Whether or not there is another identifiable cause.

All local (injection site) reactions will be considered causally related to vaccination. All malaria cases will be reported as not related to vaccination. Asymptomatic parasitemia (positive BS without related malaria clinical symptoms) will not be reported as an AE. Clinical malaria will be reported as an AE.

Reports will further classify AEs as follows:

- Related - all AEs that are assessed as definitely, probably, or possibly related.
- Unrelated - all AEs assessed as unlikely or definitely not related.

When reporting to regulatory authorities and IRB/EC is needed, AE relationship will be determined as noted above.

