### 17.2.2 Secondary Objectives

To assess vaccine efficacy of Pfs230D1M-EPA/AS01 against *P. falciparum* infection measured by BS (All Arms except Arms 3e/3f)

The vaccine efficacy will be assessed by comparing the rates of positive BS in children 5-18 years of age receiving Pfs230D1M-EPA/AS01 vs those receiving the comparator vaccines. An additional measure of vaccine protection will be assessed in the participants 1-4 years of age in Arms 4a/4b by comparing the rates of positive BS in the compounds receiving Pfs230D1M-EPA/AS01 vs those receiving the comparator vaccines.

To assess safety and reactogenicity of administration of Pfs230D1M-EPA/AS01 (All Arms)

- The frequency of systemic and local AEs will be summarized.
- A line listing of each clinical and laboratory AE classified as local, solicited, or other will be displayed in tables stratified by vaccine allocation.
- AEs will be summarized by severity and relationship to vaccine.
- The proportion of subjects with at least 1 AE will be compared by study group, and tests will be performed to assess whether these groups differ with respect to these proportions. To evaluate the difference in AEs between the initial vaccination and the subsequent vaccinations, a WSRT will be performed, where the response for each subject is the difference between the numbers of AEs in the 7 days following each vaccination. To compare number and severity of AEs between control and vaccine arms, the Wilcoxon-Mann-Whitney test (WMW, also known as Wilcoxon rank sum test and Mann-Whitney U test) as well as linear regression may be used.
- SAEs occurring within the study period will be listed by relationship to vaccine.

ELISA and SMFA assays will be conducted on a subset of samples deemed to be of scientific interest by DSF or BS assays due to the intensive laboratory analysis required to generate the data. Analysis of these data will take into account the compound randomization.

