**Study Day 784 (PILOT) + 728 (MAIN) ( $\pm 56$  days; 336 days after Vaccination #4)**

1. Perform basic history and focused physical examination, emphasizing examination of any acute complaints.
2. Record vital signs (blood pressure, temperature, and heart rate).
3. Record AEs and concomitant medications, if applicable.
4. Obtain approximately 6 mL of blood for malaria blood smear, malaria PCR, anti-Pfs230 antibody ELISA and standard membrane feeding assay (SMFA).

**Arms 1a/1b (PILOT), 3c/3d (MAIN) (9-18 year olds):  
3 Vaccinations (0, 1, 4 months—PILOT; 0, 1, 2 months—MAIN)**

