**Study Day 602 (PILOT) + 546 (MAIN) ( $\pm 28$  days; 154 days after Vaccination #4)**

1. Perform basic history and focused physical examination, emphasizing examination of any acute complaints.
2. Record vital signs (blood pressure, temperature, and heart rate).
3. Record AEs and concomitant medications, if applicable.
4. Obtain approximately 1 mL of blood for malaria blood smear and malaria PCR.
5. Scheduled unblinding of VU
  - a. If received Pfs230D1M-EPA/ASO1 offer meningitis comparator vaccination

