**Study Day 616 (PILOT) + 560 (MAIN) ( $\pm 7$  days; 168 days after Vaccination #4)**

1. Perform basic history and focused physical examination, emphasizing examination of any acute complaints.
2. Record vital signs (blood pressure, temperature, and heart rate).
3. Record AEs and concomitant medications, if applicable.
4. Obtain approximately 7 mL of blood for malaria blood smear, malaria PCR, anti-Pfs230 antibody ELISA, standard membrane feeding assay (SMFA), and transcriptional analysis.

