**Study Day 588 (PILOT) + 518 (MAIN) ( $\pm$ 56 days; 336 days after Vaccination #4)**

1. Perform basic history and focused physical examination, emphasizing examination of any acute complaints.
2. Record vital signs (blood pressure, temperature, and heart rate).
3. Record AEs and concomitant medications, if applicable.
4. Obtain approximately 6 mL of blood for malaria blood smear, malaria PCR, anti-Pfs230 antibody ELISA, standard membrane feeding assay (SMFA).

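### Only Pfs230 recipients are offered an extra meningitis vaccine at unblinding, and the between-arm AE comparison has no window or cut-off that keeps its reactions out

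*Combined protocol and SAP*

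**What the plan says.** Appendix B schedules unblinding of the vaccine unit at "154 days after Vaccination #4", which is Day 546 in the main phase and Day 602 in the pilot. At that visit staff are told: "If received Pfs230D1M-EPA/ASO1 offer meningitis comparator vaccination". The same line appears for the 5-8 year arms, the 9-18 year arms and the adults. No matching injection is offered to comparator recipients, who had Menactra as their third dose (Day 56 main, Day 126 pilot).

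Section 10.2 times the offer differently: the meningitis "vaccine will also be offered to participants randomized to the Pfs230 arms at the end of the study". Appendix B still has visits to come. For children the next one, 14 days later, carries the instruction "Record AEs and concomitant medications, if applicable", and the last is "336 days after Vaccination #4".

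Section 15.3 keeps unsolicited AEs, SAEs and new chronic illnesses under recording beyond the first 7 days after a vaccination and gives no end date. Section 15.3.2 adds: "All local (injection site) reactions will be considered causally related to vaccination". It does not say which product.

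Section 17.2.2 compares by group the share of participants with any AE, and the number and severity of AEs. Section 17.1.1 does the same for the pilot, and 17.3.1.1 adds Fisher's exact tests. None of these comparisons has a stated period. The one windowed analysis is the within-subject signed rank test on the 7 days after each vaccination. SAEs have their own line: "SAEs occurring within the study period will be listed by relationship to vaccine".

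**The concern.** The safety question is how Pfs230D1M-EPA/AS01 compares with the comparator schedule. From the unblinding visit onwards the arms differ in a second way: one is offered a fifth injection, given openly, and the other is not. A programmer applying 17.1.1 and 17.2.2 literally would have no rule for leaving out events that follow that injection. Severity and relatedness would also be judged by people who know the assignment.

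Safety is a secondary objective in the main study and a primary objective in the pilot, where there are only 15 children per arm in each age group and the same offer is made at Day 602. The measures most exposed are AE counts, related AEs and local AEs. For a late SAE or new chronic illness, an unrecorded suspected product would make the causality call harder.

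**Working it through.** **Timing.** Dose 4 is at Day 392 (main) or 448 (pilot), and the unblinding visit is at Day 546 or 602.
- Unblinding: 546 − 392 = 154 and 602 − 448 = 154 days after dose 4, which reproduces the plan's figure.
- Last visit: 728 − 392 = 336 and 784 − 448 = 336 days after dose 4.
- Gap: 336 − 154 = 182 days, or 182/336 = 54% of follow-up after dose 4. With the visit windows of ±28 and ±56 days it runs from 98 to 266 days.
- In the 9-18 year arms the last visit is headed "Study Day 588 (PILOT) + 518 (MAIN" but described as 336 days after dose 4. The arithmetic above gives 784 and 728, so the day label is wrong.

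**Inputs for size.** The documents give no reaction rate for MenAfriVac, the product named in 10.2. As a stand-in I use the adult trial's Menactra arm in Table 5: local reactions in 14 of 80, or 18%. Section 3.3 reports 1,101 participants with at least one vaccination. Assuming equal allocation, about 550 are Pfs230 recipients. Uptake is not stated, so I take u = 50% to 100%.

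**Share with any AE.** The added share is (1 − p) × 0.18 × u.
- At p = 94% (adult control arm, Table 3): 0.06 × 0.18 × 0.5 = 0.5 points, and 0.06 × 0.18 × 1 = 1.1 points.
- At p = 98% (adult full-dose Pfs230 arm): 0.2 to 0.4 points.

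**Share with any local reaction.** The background that matters is that of the arm receiving the extra dose. The adult full-dose arm had 91%, so the addition is at most 0.09 × 0.18 = 1.6 points.

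**Local AE counts.**
- Background in the Pfs230 arm: 111/56 over the primary series (Table 3) plus 53/82 after the booster (Table 5) = 1.98 + 0.65 = 2.63 per person, or about 1,450 for 550 people.
- Extra, at one reaction per reactor: 0.18 × 550 × u = 50 to 99.
- Ratio: 50/1,450 = 3% to 99/1,450 = 7%. Counting events instead (17 in 80) gives 58 to 117, or 4 to 8%, which is the same order.

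**Capture.** Table 5 reports reactions within seven days. Appendix B has no day 1, 3 or 7 visit after the extra dose. The next visit is 14 days later for children and, for adults, Day 644, which is 644 − 546 = 98 days later. Short-lived reactions would reach the database only as unsolicited reports, so the figures above are the upper end.

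**The case against.** The strongest reply is that the plan never says the whole study period is compared by arm. That is correct. A reader might infer it from the missing window, but the phrase about the study period governs only the SAE listing, which is not a test. The text therefore supports saying that later reactions could be counted against Pfs230, not that they will be.

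Three more points stand. First, the comparator arm already carries its own Menactra reactions in its total, so the imbalance is five injections against four, not some against none. Secondly, the extra injections fall in the arm where local reactions are already near-universal, so no conclusion about reactogenicity is likely to turn on them. Applying the 18% rate to the comparator's 26% background gives a larger shift (0.74 × 0.18 = 13.3 points), but that is the wrong arm's background. Thirdly, 15.3.2 uses timing as a causality criterion, so an injection-site reaction the day after the extra dose would hardly be ascribed to one given 154 days earlier.

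A reader might also link this to the meningitis imbalance described in section 5.1. The documents do not support that step: they report it for RTS,S with no clear relationship identified, and the comparator arm has had meningococcal vaccine since dose 3, so that difference predates unblinding.

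Section 15.4 illustrates the follow-up period as 3 months after the last vaccination, which would place the offer outside it, while 8.3 says at least 12 months. This does not answer the concern. It shows that the period is unsettled.

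**Conclusion.** The point holds as a gap in the analysis plan with a known one-sided treatment inside it. The offer to one arm, its timing and the continued AE recording are explicit; the absence of any cut-off is plain from 17.1.1 and 17.2.2. The bias is small: about 0.5 to 1.1 points on any AE at a 94% background, and about 3 to 7% of local AE counts. That rests on adult Menactra data standing in for MenAfriVac in children and adults, on adult Pfs230 reaction rates, on equal allocation, and on 50 to 100% uptake.

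It does not support a claim that the safety conclusions are unreliable, or that late events cannot be attributed. It is still worth correcting before analysis, because the correction is cheap and removes a source of AEs that has nothing to do with the study vaccine.

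**What to change.** In 17.1.1 and 17.2.2, state that the primary between-arm AE comparison ends, for every participant in both arms, at the vaccine unit's unblinding visit. Report later AEs, SAEs and new chronic illnesses separately, by arm and by whether the post-unblinding meningitis vaccine was received. Keep a comparison of SAEs and new chronic illnesses over the whole follow-up as a sensitivity analysis, so that late serious events are still shown by arm. Add a field for the suspected product to each related AE after that visit.

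Reconcile the following:
- the timing of the offer in 10.2 with Appendix B;
- the follow-up period in 8.3 with the example in 15.4;
- the mislabelled last visit for the 9-18 year arms;
- for adults, the Day 546 visit in Appendix B with Appendix A, whose Year 2 columns go from Day 504 to Day 560.

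The cost is a few sentences and one case report form field. The downside is that about six months of non-serious AE data become descriptive.

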**Study Day 616 (PILOT) + 560 (MAIN) ( $\pm 7$  days; 168 days after Vaccination #4)**

1. Perform basic history and focused physical examination, emphasizing examination of any acute complaints.
2. Record vital signs (blood pressure, temperature, and heart rate).
3. Record AEs and concomitant medications, if applicable.
4. Obtain approximately 7 mL of blood for malaria blood smear, malaria PCR, anti-Pfs230 antibody ELISA, standard membrane feeding assay (SMFA), and transcriptional analysis.

**Study Day 700 (PILOT) + 644 (MAIN) ( $\pm$ 56 days; 252 days after Vaccination #4)**

1. Perform basic history and focused physical examination, emphasizing examination of any acute complaints.
2. Record vital signs (blood pressure, temperature, and heart rate).
3. Record AEs and concomitant medications, if applicable.
4. Obtain approximately 6 mL of blood for malaria blood smear, malaria PCR and, anti-Pfs230 antibody ELISA, standard membrane feeding assay (SMFA).

**Study Day 588 (PILOT) + 518 (MAIN) ( $\pm$ 56 days; 336 days after Vaccination #4)**

1. Perform basic history and focused physical examination, emphasizing examination of any acute complaints.
2. Record vital signs (blood pressure, temperature, and heart rate).
3. Record AEs and concomitant medications, if applicable.
4. Obtain approximately 6 mL of blood for malaria blood smear, malaria PCR, anti-Pfs230 antibody ELISA, standard membrane feeding assay (SMFA).

## **Arms 3e/3f (Adults 19 years of age and older): 3 Vaccinations (0, 1, 2 months)**

### **Study Day -7 ( $\pm 7$ days; Drug Treatment Visit)**

1. Perform basic history and focused physical examination, emphasizing examination of any acute complaints.
2. Record vital signs (blood pressure, temperature, and heart rate).
3. Record AEs and concomitant medications, if applicable.
4. Obtain approximately 7.5 mL of blood for CBC with differential and platelet count, ALT, creatinine, hemoglobin typing, malaria blood smear and malaria PCR, and transcriptional analysis.
5. For females, obtain a urine or serum sample for  $\beta$ -hCG testing. Ensure that the test is negative before proceeding.
6. For females, ensure agreement and compliance with pregnancy prevention before AL dosing.
7. Administer first dose of artemether/lumefantrine (AL).
  - a. Additional doses of AL will occur on study days -6, -5

### **Study Day 0 (day of Vaccination #1)**

The following evaluations/procedures will be completed before vaccination:

1. Verify that informed consent was obtained.
2. Ensure that all inclusion/exclusion criteria are met.
3. Ensure that CBC, ALT, creatinine, HIV, and urine results from screening are within protocol-defined limits (see Exclusion Criteria above) before vaccinating
4. Perform basic history and focused physical examination, emphasizing examination of any acute complaints.
5. Record vital signs (blood pressure, temperature, and heart rate).
6. During the physical examination, study staff will educate the subject regarding signs and symptoms of potential adverse events (AEs) and indications for use of antipyretics if fever, headache, or malaise occurs.
7. For females, obtain a urine or serum sample for  $\beta$ -hCG testing. Ensure that the test is negative before vaccinating.
8. For females, ensure agreement and compliance with pregnancy prevention before vaccinating.
9. Confirm that all criteria for vaccination have been met according to inclusion/exclusion criteria
10. Confirm continued eligibility to receive vaccination
11. Obtain approximately 17.5 mL of blood for CBC with differential and platelet count, ALT, creatinine, malaria blood smear, malaria PCR, anti-Pfs230 antibody ELISA, and standard membrane feeding assay (SMFA), and transcriptional analysis.
12. Administer the vaccine.

The following evaluations/procedures will be completed following vaccination:

1. Observe the subject for at least 30 minutes after vaccination to evaluate immediate adverse reactions.
2. Record vital signs (blood pressure, temperature, and heart rate).
3. Perform interim history and physical examination, focusing on any acute complaints.
4. Record AEs and concomitant medications, if applicable.

**Study Day 1 ( $\pm 0$  days; 1 day after Vaccination #1)**

1. Perform basic history and focused physical examination (including injection site), emphasizing examination of any acute complaints.
2. Record vital signs (blood pressure, temperature, and heart rate).
3. Record AEs and concomitant medications, if applicable.

**Study Day 3 ( $\pm 1$  day; 3 days after Vaccination #1)**

1. Perform basic history and focused physical examination (including injection site), emphasizing examination of any acute complaints.
2. Record vital signs (blood pressure, temperature, and heart rate).
3. Record AEs and concomitant medications, if applicable.
4. Obtain approximately 6.0 mL of blood for CBC with differential and platelet count, ALT, creatinine, and transcriptional analysis.

**Study Day 7 ( $\pm 2$  days; 7 days after Vaccination #1)**

1. Perform basic history and focused physical examination (including injection site), emphasizing examination of any acute complaints.
2. Record vital signs (blood pressure, temperature, and heart rate).
3. Record AEs and concomitant medications, if applicable.

**Study Day 14 ( $\pm 3$  days; 14 days after Vaccination #1)**

1. Perform basic history and focused physical examination, emphasizing examination of any acute complaints.
2. Record vital signs (blood pressure, temperature, and heart rate).
3. Record AEs and concomitant medications, if applicable.
4. Obtain approximately 11.5 mL of blood for CBC with differential and platelet count, ALT, creatinine, malaria blood smear, malaria PCR, anti-Pfs230 antibody ELISA and standard membrane feeding assay (SMFA).

**Study Day 28 ( $\pm 7$  days; day of Vaccination #2)**

The following evaluations/procedures will be completed before vaccination:

1. Perform interim history and physical examination, focusing on any acute complaints.
2. Record vital signs (blood pressure, temperature, and heart rate).
3. During the physical examination, study staff will educate the subject regarding signs and symptoms of potential adverse events (AEs) and indications for use of antipyretics if fever, headache, or malaise occurs.
4. Obtain approximately 11.5 mL of blood for CBC with differential and platelet count, ALT, creatinine, malaria blood smear, malaria PCR, anti-Pfs230 antibody ELISA, and standard membrane feeding assay (SMFA).
5. For females, obtain a urine or serum sample for  $\beta$ -hCG testing. Ensure that the test is negative before vaccinating.
6. For females, ensure agreement and compliance with pregnancy prevention before vaccinating.
7. Confirm continued eligibility to receive vaccination.
8. Administer the vaccine.

The following evaluations/procedures will be completed following vaccination:

1. Observe the subject for at least 30 minutes after vaccination to evaluate immediate adverse reactions.
2. Record vital signs (blood pressure, temperature, and heart rate).
3. Perform interim history and physical examination, focusing on any acute complaints.
4. Record AEs and concomitant medications, if applicable.

**Study Day 29 ( $\pm 0$  days; 1 day after Vaccination #2)**

1. Perform basic history and focused physical examination (including injection site), emphasizing examination of any acute complaints.
2. Record vital signs (blood pressure, temperature, and heart rate).
3. Record AEs and concomitant medications, if applicable.

**Study Day 31 ( $\pm 1$  day; 3 days after Vaccination #2)**

1. Perform basic history and focused physical examination (including injection site), emphasizing examination of any acute complaints.
2. Record vital signs (blood pressure, temperature, and heart rate).
3. Record AEs and concomitant medications, if applicable.
4. Obtain approximately 6.0 mL of blood for CBC with differential and platelet count, ALT, creatinine, and transcriptional analysis.

**Study Day 35 ( $\pm 2$  days; 7 days after Vaccination #2)**

1. Perform basic history and focused physical examination (including injection site), emphasizing examination of any acute complaints.
2. Record vital signs (blood pressure, temperature, and heart rate).
3. Record AEs and concomitant medications, if applicable.

**Study Day 42 ( $\pm 28$  days; 14 days after Vaccination #2)**

1. Perform basic history and focused physical examination, emphasizing examination of any acute complaints.
2. Record vital signs (blood pressure, temperature, and heart rate).
3. Record AEs and concomitant medications, if applicable.
4. Obtain approximately 11.5 mL of blood for CBC with differential and platelet count, ALT, creatinine, malaria blood smear, malaria PCR, anti-Pfs230 antibody ELISA and standard membrane feeding assay (SMFA).

**Day 56 ( $\pm 56$  days; day of Vaccination #3)**

The following evaluations/procedures will be completed before vaccination:

1. Perform interim history and physical examination, focusing on any acute complaints.
2. Record vital signs (blood pressure, temperature, and heart rate).
3. During the physical examination, study staff will educate the subject regarding signs and symptoms of potential adverse events (AEs) and indications for use of antipyretics if fever, headache, or malaise occurs.
4. For females, obtain a urine or serum sample for  $\beta$ -hCG testing. Ensure that the test is negative before vaccinating.

5. For females, ensure agreement and compliance with pregnancy prevention before vaccinating.
6. Obtain approximately 11.5 mL of blood for CBC with differential and platelet count, ALT, creatinine, malaria blood smear, malaria PCR, anti-Pfs230 antibody ELISA, and standard membrane feeding assay (SMFA).
7. Confirm continued eligibility to receive vaccination
8. Administer the vaccine.

The following evaluations/procedures will be completed following vaccination:

1. Observe the subject for at least 30 minutes after vaccination to evaluate immediate adverse reactions.
2. Record vital signs (blood pressure, temperature, and heart rate).
3. Perform interim history and physical examination, focusing on any acute complaints.
4. Record AEs and concomitant medications, if applicable.

